#### **14.1.36 Incomplete dates for last known date patient alive or death**

All dates must be completed with day, month and year. If the day is missing, the 15th of the month will be used for incomplete death dates or dates of last contact.

#### **14.1.37 Non-target lesion response**

If no non-target lesions are identified at baseline (and therefore not followed throughout the study), the non-target lesion response at each assessment will be considered 'not applicable (NA)'.

#### **14.1.38 Study/project specific programming**

The standard analysis programs need to be adapted for each study/project.

#### **14.1.39 Censoring reason**

In order to summarize the various reasons for censoring, the following categories will be calculated for each time to event variable based on the treatment completion page, the study evaluation completion page and the survival page.

For survival the following censoring reasons are possible:

- Alive
- Lost to follow-up

For PFS and TTP (and therefore duration of responses) the following censoring reasons are possible:

- Ongoing without event
- Lost to follow-up
- Withdraw consent
- Adequate assessment no longer available\*
- Event documented after two or more missing tumor assessments (optional, see [Table 14-5](#))
- Death due to reason other than underlying cancer (*only used for TTP and duration of response*)
- Initiation of new anti-cancer therapy

\*Adequate assessment is defined in [Section 14.1.25](#). This reason is applicable when adequate evaluations are missing for a specified period prior to data cut-off (or prior to any other censoring reason) corresponding to the unavailability of two or more planned tumor assessments prior to the cut-off date. The following clarifications concerning this reason should also be noted:

- This may be when there has been a definite decision to stop evaluation (e.g. reason="Sponsor decision" on study evaluation completion page), when patients are not followed for progression after treatment completion or when only UNK assessments are available just prior to data cut-off).
- The reason "Adequate assessment no longer available" also prevails in situations when another censoring reason (e.g. withdrawal of consent, loss to follow-up or alternative anti-cancer therapy) has occurred more than the specified period following the last adequate assessment.
- This reason will also be used to censor in case of no baseline assessment.

1.1 Study design

This is a prospectively designed, multicenter, open-label, phase II study to evaluate the efficacy and safety of single-agent INC280. NSCLC patients with stage IIIB or IV that are EGFR wild-type (for exon 19 deletions and exon 21 L858R substitution mutations) and ALK-negative rearrangement will be pre-screened for MET amplification and MET mutation status. Enrolled patients will be assigned to the following nine cohorts:

- Cohort 1: Pre-treated patients with MET GCN \geq 6, including:
 - Cohort 1a: Patients with a MET GCN of \geq 10, or
 - Cohort 1b: Patients with a MET GCN of \geq 6 and $<$ 10, or
- Cohort 2: Pre-treated patients with MET GCN \geq 4 and $<$ 6, or
- Cohort 3: Pre-treated patients with MET GCN $<$ 4, or
- Cohort 4: Pre-treated patients with MET mutations regardless of MET GCN, or
- Cohort 5: Treatment-naïve patients with MET dysregulation, including:
 - Cohort 5a: Patients with a MET GCN \geq 10, or
 - Cohort 5b: Patients with MET mutations regardless of MET GCN
- Cohort 6: Pre-treated patients with either MET GCN \geq 10 without MET mutations or MET mutations regardless of MET GCN
- Cohort 7: Treatment-naïve patients with MET mutations regardless of MET GCN

Primary diagnostic of MET amplification (and ALK rearrangement, if applicable) will be performed using fluorescence in situ hybridization (FISH) and for MET mutations by RT-PCR at a Novartis-designated central laboratory. [REDACTED]

[REDACTED]

[REDACTED]

Enrolled patients will be treated with INC280 tablets at 400 mg twice daily (BID). Treatment with INC280 will continue until patient experiences any of the following: disease progression according to RECIST 1.1 as determined by investigator and confirmed by BIRC, unacceptable toxicity that precludes further treatment, treatment is discontinued at the discretion of the Investigator or patient, lost to follow-up, or death. Treatment with INC280 may be continued beyond RECIST 1.1-defined PD (as determined by investigator and confirmed by BIRC) if, in

the judgment of the investigator, there is evidence of clinical benefit and the patient wishes to continue on the study treatment.

Approximately 456 patients (69 patients per each Cohort 1a, 1b, 2, 3, 4; 27 patients per each Cohort 5a, 5b; approximately 30 patients in Cohort 6 and approximately 27 patients in Cohort 7) were to be enrolled in the study if none of the five cohorts (Cohort 1a, 1b, 2, 3, 4) are stopped for futility at the time of the interim analysis. No interim analysis is planned for Cohorts 5a, 5b, 6 and 7.

The primary analysis will be conducted when all treated patients in their respective cohort (if not stopped for futility at interim analysis) have completed at least 6 cycles of treatment (18 weeks) or discontinued treatment earlier. Due to the expected difference in enrollment rate for each cohort, the primary analysis for the different cohorts may occur at different times. The primary analysis for any cohort that was stopped for futility may be combined with the primary analyses for other cohorts. Also, if majority of the patients in a cohort meet the required follow-up time for primary analysis, the primary analysis of such cohorts may be combined with the primary analyses for other cohorts.

1.2 Objectives

1.2.1 Primary objective

[figure not shown]
The primary objective is to evaluate the antitumor activity of INC280, as measured by overall response rate (ORR) by Blinded Independent Review Committee (BIRC) assessment, by cohort.

1.2.2 Secondary objectives

Key secondary objective is to evaluate duration of response (DOR) as assessed by BIRC, by cohort.

Other secondary objectives are:

- To evaluate ORR and DOR by investigator assessment, by cohort
- To evaluate time to response (TTR), disease control rate (DCR) and progression-free survival (PFS) by investigator and by BIRC assessment, by cohort
- To evaluate overall survival (OS), by cohort
- To evaluate INC280 safety profile as monotherapy in NSCLC patients with advanced/metastatic setting
- To characterize the pharmacokinetics of INC280 and metabolite CMN288

2 Statistical methods

This section and its subsections will be imported to section 9.7 of the CSR after the analyses have been conducted. This section of the SAP follows the CSR template structure of Section 9.7 as of the release date of this document.

The text will be changed to the past tense when imported into the CSR; references to [Section 4](#) of the SAP, where additional details are provided for programming implementation, may be removed in the CSR.

In what follows, study drug refers to INC280.

2.1 Data analysis general information

Data will be analyzed by Novartis Biostatistics and Statistical Programming personnel according to the data analysis section 10 of the CINC280A2201 protocol, which will be available in Appendix 16.1.1 of the Clinical Study Report (CSR). Important information is given in the following sections and details are provided, as applicable, in [Section 4](#) from which Appendix 16.1.9 of the CSR will be extracted.

SAS® version 9.4 (or later version if available at time of database lock) will be used in all analyses.

Data from all patients who signed informed consent in centers that participate in this study will be used in the analysis. Data collected after withdrawal of informed consent will not be reported. Data collected on the same date as withdrawal of informed consent are reported. Due to expected small size of enrollment at individual centers, no center effect will be assessed. Each analysis will use all data in the database up to the analysis cutoff date, determined prior to database lock.

The data from all participating centers in this protocol will be combined. For cohorts 1-4, the efficacy data for each cohort will be analyzed separately at the time of the interim analysis and one (or more) of the cohorts may be stopped for futility according to the criteria described in the Interim Analysis Section of the study protocol (Section 10.7). No interim analysis for futility is planned for Cohorts 5a, 5b, 6 and 7.

Previous reports

- The primary analyses for MET mutant patients (Cohort 4, and 5b) and for all closed cohorts for futility (Cohorts 1b, 2, and 3) were conducted based on data with a data cut-off date of 15-Apr-2019.
- The primary analyses for MET amplified patients with a MET GCN ≥ 10 (Cohorts 1a and 5a) and pre-treated expansion cohort (Cohort 6) were conducted based on data with a data cut-off date of 06-Jan-2020.
- A preliminary analysis for MET mutant patients (expansion Cohort 7) along with updated results from other MET mutant cohorts (Cohorts 4, 5b and 6) was conducted based on data with a data cut-off date of 18-Sep-2020.
- The primary analyses for MET mutant patients (expansion Cohort 7) along with updated results from other MET mutant cohorts (Cohorts 4, 5b and 6) was conducted based on data with a data cut-off date of 30-Aug-2021.

Planned analyses for this report

- The updated analyses for **all MET mutant patients** (Cohorts 4, 5b and 6, and 7) will be conducted when Last Patient Last Visit is reached.
- Data from cohorts (Cohort 1-7) will be included for patient disposition, baseline characteristics and safety analyses. Patient disposition, baseline characteristics and safety analyses will also be presented combining the MET mutant patients (pre-treated, treatment-naïve and all MET mutant patients) and all amplified patients (complementary subgroup to MET mutant patients).
- Data from MET mutant cohorts (Cohort 4, 5b, 6 and 7) will be included for efficacy a [REDACTED] They will also presented combining the MET mutant patients (pre-treated and treatment-naïve MET mutant patients).
- No PK analyses will be included in this report as no additional PK samples are analyzed at this time.

[REDACTED]

All available data from all patients will be summarized in the final Clinical Study Report (CSR).

[Section 4.1](#) provides further details regarding data to be included in the analyses.

General presentation of descriptive summaries

Qualitative data (e.g., gender, race) will be summarized by frequency counts and percentages. Percentages will be calculated using the number of patients in the relevant population or subgroup as the denominator.

Continuous data (e.g., age, body weight) will be summarized by appropriate descriptive statistics (i.e. mean, standard deviation, median, minimum, and maximum).

2.2 Analysis sets

Screened patients

Patients are considered to be enrolled into the study if they have signed main informed consent. Only patients who have signed main informed consent will be included in the analysis data sets.

Patients are considered to be a screen failure if they have signed main informed consent but failed to be treated.

Patients are considered to be a pre-screen failure if they have failed to meet pre-screened criteria i.e. they have not signed main informed consent.

Full Analysis Set

The Full Analysis Set (FAS) includes all patients who received at least one dose of INC280. The FAS will be used for all listings. Unless otherwise specified the FAS will be the default analysis set used for all efficacy analyses.

Safety Set

The Safety Set includes all patients who received at least one dose of INC280. All safety data will be analyzed using the Safety Set.

The FAS and Safety Set in this study are identical.

Per-Protocol Set

The Per-Protocol Set (PPS) consists of a subset of patients in the FAS who have no major protocol deviations, regardless of the adequate tumor assessment.

The major protocol deviations that will lead to removal of patients from the PPS are listed below:

- Patient does not have Stage IIIB or IV NSCLC (any histology) at the time of study entry
- Patient does not have a histologically or cytologically confirmed diagnosis of non-squamous NSCLC with EGFR wt status (for exon 19 deletions and exon 21 L858R substitution mutations)
- Patient with NSCLC of pure squamous cell histology that has known EGFR mutations in exons 19 or 21 is enrolled
- Patient without MET status for eligibility as determined by central assessment at a Novartis designated laboratory prior to first dose
- Patient has not received one or two prior lines of systemic therapy for advanced/metastatic disease (only for cohorts 1a, 1b, 2, 3 and 4)
- Patient has received prior systemic therapy for advanced/metastatic disease (only for cohorts 5a and 5b and 7)
- Patient has not received one prior line of systemic therapy for advanced/metastatic disease (only for cohort 6)
- Patients has no measurable lesion from RECIST 1.1 evaluation at baseline or has no baseline evaluation

- Patient has received crizotinib, or any other MET or HGF inhibitor before entering screening
- Patient has characterized ALK-positive rearrangement or un-determinant ALK rearrangement status at study entry
- ECOG performance status > 1 at study entry
- Presence or history of a malignant disease other than NSCLC that has been diagnosed and/or required therapy within the past 3 years. Exceptions to this exclusion include the following: completely resected basal cell and squamous cell skin cancers, and completely resected carcinoma in situ of any type

Combined cohorts

Patient disposition, baseline characteristics, exposure and safety analyses will be presented combining the MET mutant cohorts per line of treatment and regardless of the line of treatment, and all amplified cohorts whereas [REDACTED] efficacy will be presented combining the MET mutant cohorts per line of treatment.

The combined cohorts are defined as follows:

- *All patients (2/3L, MET mutant) (N=100)*: Pretreated patients from Cohort 4 and subset of MET mutant patients from Cohort 6.
- *All patients (1L, MET mutant) (N=60)*: Treatment-naïve patients from Cohort 5b and 7.
- *All MET mutant patients (N=160)*: All MET mutant patients regardless of the line of treatment i.e. Pre-treated MET mutant patients (2/3L, MET mutant) and treatment-naïve MET mutant patients (1L, MET mutant) as defined above.
- *All Amplified patients (N=213)*: All patients enrolled in cohorts other than MET mutant cohorts (Cohorts 1a, 1b, 2, 3, 5a and subset of amplified patients from Cohort 6).
- All patients (N=373): All patients enrolled in the study.

Subgroup analysis

Efficacy

ORR, DOR, PFS by BIRC and investigator assessment will be summarized for the following subgroups:

- age group (< 65 years, \geq 65 years)
- gender (male, female)
- race (Caucasian, Asian, Others)
 - *Others: include Black, Other, Unknown, Native American*
- ECOG performance status (0, \geq 1)

Safety

Adverse events (AEs) will be summarized for the following subgroups:

CONFIDENTIAL - For Business Use Only

- age group (< 65 years, \geq 65 years)
- gender (male, female)
- race (Caucasian, Asian, Others)
- ECOG performance status (0, \geq 1)
- Patients with long exposure of study drug (at least 48, 72, 96 weeks of exposure)

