## 5.2 Inclusion criteria

Patients eligible for inclusion in this study have to meet **all** of the following criteria:

Written informed consent must be obtained prior to any screening procedures

1. Age  $\geq$  18 years
2. Stage IIIB or IV NSCLC (any histology) at the time of study entry
3. Histologically or cytologically confirmed diagnosis of NSCLC that is:
  - a. EGFR wt. This should have been assessed as part of the patient standard of care by a validated test for EGFR mutations, as per the Molecular Testing Guideline for Selection of Lung Cancer Patients for EGFR and ALK Tyrosine Kinase Inhibitors from College of American Pathologists, International Association for the Study of Lung Cancer, and Association for Molecular Pathology ([Lindeman et al 2013](#)). The EGFR wt status (for exon 19 deletions and exon 21 L858R substitution mutations) must be documented in the patient source documents before the patient can be consented for pre-screening for cMET amplification and cMET mutation status (except for patients who are treatment-naïve potentially eligible for Sub-Cohort 5a, 5b and Cohort 7 or if molecular pre-screening will be performed by NGS and local status is not available). Patients with NSCLC of pure squamous cell histology can enter pre-screening without EGFR mutation testing or result, however patients with pure squamous cell histology and are known to have EGFR mutations in exons 19 or 21 will be excluded,
  - b. AND ALK rearrangement -negative. This should have been assessed as part of the patient standard of care by a validated test. The ALK rearrangement-negative status must be documented in the patient source documents before the patient can be consented for pre-screening for cMET amplification and cMET mutation status, except for patients who are treatment-naïve potentially eligible for Sub-Cohorts 5a, 5b and Cohort 7; if local ALK testing is not available, patient status will be determined centrally along with the cMET status. Patients with NSCLC of pure squamous cell histology can enter pre-screening without ALK testing or result, however patients with pure squamous cell histology that are known to have ALK rearrangement will be excluded.
  - c. AND (as determined by central assessment at a Novartis designated laboratory) either:
    - Cohort 1: Pre-treated patients with cMET GCN  $\geq$  6, including:
      - Sub-cohort 1a: Patients with cMET GCN of  $\geq$ 10, or

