### 10.1.3 Per-Protocol Set

The Per-Protocol Set (PPS) consists of a subset of patients in the FAS who have no major protocol deviations, who have an adequate tumor assessment at baseline and have a follow-up tumor assessment > 5 weeks after starting treatment (unless PD is observed before that time).

All major protocol deviations leading to exclusion from the PPS will be detailed in the Reporting and Analysis Plan (RAP).

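### If coded literally, the second Per-Protocol exclusion in SAP 2.2 removes eligible squamous patients, and the ALK exclusion may do the same for untested pure squamous patients

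*SAP*

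**What the plan says.** Protocol 5.2 sets the eligible population. Criterion 2 is "Stage IIIB or IV NSCLC (any histology) at the time of study entry". Criterion 3a requires EGFR wild-type status but adds that "Patients with NSCLC of pure squamous cell histology can enter pre-screening without EGFR mutation testing or result"; such patients are excluded only if a mutation in exon 19 or 21 is known. Criterion 3b requires ALK-negative status, says that "if local ALK testing is not available, patient status will be determined centrally along with the cMET status", and adds that "Patients with NSCLC of pure squamous cell histology can enter pre-screening without ALK testing or result"; again, only a known rearrangement excludes them.

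Protocol 10.1.3 leaves the list of deviations that remove a patient from the PPS to the analysis plan. SAP 2.2 gives that list. Its first item repeats that any histology is acceptable. The second is "Patient does not have a histologically or cytologically confirmed diagnosis of non-squamous NSCLC with EGFR wt status", for exon 19 deletions and exon 21 L858R. The third is "Patient with NSCLC of pure squamous cell histology that has known EGFR mutations in exons 19 or 21 is enrolled". A later item is "Patient has characterized ALK-positive rearrangement or un-determinant ALK rearrangement status at study entry", with no reference to histology and no definition of the undetermined category.

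SAP 4.2 (Table 4-1) points back to this list as the PPS rule. ORR by BIRC (SAP 2.7.4), DOR by BIRC and PFS (both SAP 2.8.1) are repeated on the PPS, and SAP 2.4 tabulates major deviations by cohort. The primary analysis is on the Full Analysis Set (SAP 2.7.2). SAP Section 3 declares no change from the protocol-specified analyses.

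**The concern.** A Per-Protocol repeat asks whether the result survives once patients who broke the protocol in important ways are left out. It answers that question only if the patients removed did break the protocol. Someone with pure squamous NSCLC and no known EGFR or ALK alteration is eligible under the histology, EGFR and ALK criteria of Protocol 5.2, yet meets the second SAP exclusion simply by having squamous histology. If that item is programmed as written, the PPS becomes a non-squamous subset, and eligible patients appear as major deviators in the study report. Protocol 2.2.2 argues for activity in MET-mutated disease irrespective of histology, so a restriction by histology would run against the study's own rationale.

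The ALK item raises a narrower version of the same problem. The protocol lets pure squamous patients into pre-screening with no ALK result. If the undetermined category includes patients who were never tested, a result the protocol did not ask for at that stage would remove them.

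**Working it through.** **Rules side by side**

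| Patient | Protocol 5.2 | SAP 2.2, read literally |
|---|---|---|
| Non-squamous, EGFR wt, ALK-negative | Meets criteria | Kept |
| Non-squamous, EGFR wt not documented | Fails criterion 3a | Removed (second item) |
| Pure squamous, EGFR mutation known | Excluded | Removed (second and third items) |
| Pure squamous, no EGFR alteration known | Meets criteria | **Removed (second item)** |
| Pure squamous, ALK not tested | May enter pre-screening | **Removed by the ALK item if undetermined includes untested** |
| Not pure squamous, no ALK result | Fails criterion 3b | Removed (ALK item), in line with the protocol |

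The two rows in bold are the points of conflict. In the third row the patient is removed twice: if the second item already takes out all squamous patients, the third has nothing left to do. That redundancy, with the any-histology wording of the first item, indicates that the second was meant to say that non-squamous patients must be EGFR wild-type.

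**Possible size**

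The documents give no count or share of squamous patients, so any share is an assumption. A rough guide comes from the protocol's epidemiology: adenocarcinoma is 47% of NSCLC (Section 1.1.1), and MET mutations occur in 2-4% of adenocarcinomas and about 1% of other histologies (Section 1.1.3.2). The non-adenocarcinoma share of MET-mutated NSCLC is then 0.53 × 0.01 / (0.47 × a + 0.53 × 0.01):

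- a = 0.04: 0.0053 / 0.0241 = 22%
- a = 0.02: 0.0053 / 0.0147 = 36%

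Squamous disease is only part of that, so 5 to 15% is used below.

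SAP 2.1 limits efficacy in this report to the MET-mutant cohorts. Of the pooled groups in SAP 2.2, 5 to 15% is 5 to 15 of the 100 pre-treated patients and 3 to 9 of the 60 treatment-naïve patients.

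**Effect on ORR, Cohort 4 as illustration**

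Protocol 1.2.1.2.2 gives a preliminary ORR of 39.1% (27.6-51.6) in 69 patients; 0.391 × 69 = 27 responders. The exact limits are BetaInv(0.025; x, n−x+1) and BetaInv(0.975; x+1, n−x). With x = 27 and n = 69 they give 27.6 and 51.6, which reproduces the stated interval.

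| Assumed share | Removed | Removed patients respond like the rest | All removed are responders | All removed are non-responders |
|---|---|---|---|---|
| 5% | 3 | 26/66 = 39.4% (27.6-52.2) | 24/66 = 36.4% (24.9-49.1) | 27/66 = 40.9% (29.0-53.7) |
| 10% | 7 | 24/62 = 38.7% (26.6-51.9) | 20/62 = 32.3% (20.9-45.3) | 27/62 = 43.5% (31.0-56.7) |
| 15% | 10 | 23/59 = 39.0% (26.5-52.6) | 17/59 = 28.8% (17.8-42.1) | 27/59 = 45.8% (32.7-59.2) |

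The last two columns are bounds, not expectations. For Cohort 5b the stated 72.0% (50.6-87.9) is 18/25. A 15% share removes 4 patients and gives between 14/21 = 66.7% (43.0-85.4) and 18/21 = 85.7% (63.7-97.0).

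**The case against.** The best defence is that the list corrects itself. The any-histology item and the separate pure-squamous item make sense only if squamous patients without a known mutation stay in the PPS. Read as a whole, the list matches criterion 3a. SAP 4.2 also works partly from deviations entered in the database, and an eligible squamous patient should have none to enter. This largely stands as evidence of intent. It does not remove the problem, because SAP 2.2 is the text that defines these deviations. A programmer or data manager who follows the second item as written would flag squamous patients.

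On ALK, three objections carry weight. For patients not of pure squamous histology, a missing result is a genuine eligibility failure, and removing them is correct. For pure squamous patients, the exemption in Protocol 5.2 covers entry to pre-screening, whereas Protocol 7.1.1.1 requires central confirmation of ALK-negative status wherever local testing is unavailable and names no squamous exception. It is therefore not settled that such a patient could be treated without a result. And the undetermined category may mean a failed or inconclusive test rather than no test.

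A reader might infer that the PPS analyses have been, or will be, run on the wrong set. The documents do not show how the item was coded. A reader might also infer that everyone without an ALK result is wrongly removed; that does not follow for histologies other than pure squamous.

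**Conclusion.** The second PPS exclusion contradicts Protocol 5.2 as worded and makes the item after it redundant. If coded literally, it takes eligible squamous patients out of the supportive ORR, DOR and PFS analyses and counts them as major deviators. The ALK exclusion may do the same to pure squamous patients, on two conditions: that the undetermined category includes untested patients, and that the protocol does allow them to be treated without a result.

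The consequence is small. The Full Analysis Set results are untouched, and no hypothesis test rests on the PPS. The number affected is not in the documents. On an assumed 5 to 15% share it would be 3 to 10 of 69 in Cohort 4, with the ORR staying at about 39% and the interval widening slightly if the removed patients respond like the others. In the extreme, three removed patients who were all responders would put the lower limit at 24.9%, just under the 25% reference. That is a bound based on a preliminary result, and it does not suggest that the trial's conclusion is at risk. This is a wording correction worth making before the final report.

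**What to change.** In SAP 2.2, replace the second exclusion with two:

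- (a) *Patient has no histological or cytological confirmation of NSCLC.*
- (b) *Patient with NSCLC other than pure squamous histology has no documented EGFR wild-type status (exon 19 deletions and exon 21 L858R).*

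Keep the item on pure squamous patients with a known EGFR mutation. Item (a) preserves the confirmed-diagnosis requirement. The phrase *other than pure squamous* in (b) follows the protocol's exemption and places mixed histology on the side that needs a result.

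For ALK, first reconcile Protocol 5.2 with 7.1.1.1 on whether pure squamous patients need a central result before treatment. Then define the undetermined category, stating whether it includes untested patients. If pure squamous patients may be treated without a result, limit the undetermined or missing-ALK exclusion to other histologies. A known ALK rearrangement should continue to exclude any histology, so no extra squamous item is needed.

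The cost is a few lines of SAP text and a check that the deviation codes match. Earlier cut-offs (2019 to 2021, SAP 2.1) have already been reported. If any PPS tables from them used the literal rule, the final report should note the difference and how many patients it concerns.
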